## MODIFICATION HISTORY

Unique Identifier for this Version	Date of the Document Version	Author	Significant Changes from Previous Authorized Version
Draft 1.0	19May2017	[REDACTED]	Not Applicable – First Version
Draft 2.0	26Jun2017	[REDACTED]	Updated per client comments
Final 1.0	10OCT2017	[REDACTED]	Updated per client comments
Final 1.0	13Oct2017	[REDACTED]	The SAP was updated according to Shire's additional comments, previous version SAP on 13OCT2017 will be treated as a draft.

Document: \\quintiles.net\Enterprise\Apps\sasdata\SASa\sas\Shire\Teduglutide\ZXA48914\Biostatistics\Documentation\Protocol\SHP633-303\_Retrospective\_SAP\_Final\_V1.0\_20171013  
Author: [REDACTED] Version Number: Final V1.0  
Version Date: 13Oct2017

Template No: CS\_TP\_BS016 – Revision 3  
Effective Date: 01May2012

Reference: CS\_WI\_BS005

Copyright © 2012 Quintiles Transnational Corp. All rights reserved.  
The contents of this document are confidential and proprietary to Quintiles Transnational Corp. Unauthorized use, disclosure or reproduction is strictly prohibited.

## 1. LIST OF ABBREVIATIONS

AE	Adverse Event
AESI	Adverse Events of Special Interest
BMI	Body Mass Index
CDC	Centers for Disease Control and Prevention
CSR	Clinical Study Report
eCRF	Electronic Case Report Form
EOS	End of Study
ICF	Informed Consent Form
IVRS	Interactive Voice Response System
MedDRA	Medical Dictionary for Regulatory Activities
PS	Parenteral Support
PT	Preferred Term
SAE	Serious Adverse Event
SAP	Statistical Analysis Plan
SBS	Short Bowel Syndrome
SOC	System Organ Class

Document: \\quintiles.net\Enterprise\Apps\sasdata\SASa\sas\Shire\Teduglutide\ZXA48914\Biostatistics\Documentation\Protocol\SHP633-303\_Retrospective\_SAP\_Final\_V1.0\_20171013  
Author: [REDACTED] Version Number: Final V1.0  
Version Date: 13Oct2017

Template No: CS\_TP\_BS016 – Revision 3  
Effective Date: 01May2012

Reference: CS\_WI\_BS005

Copyright © 2012 Quintiles Transnational Corp. All rights reserved.  
The contents of this document are confidential and proprietary to Quintiles Transnational Corp. Unauthorized use, disclosure or reproduction is strictly prohibited.

## 2. INTRODUCTION

This document describes the rules and conventions to be used in the presentation and analysis of retrospective data for Protocol SHP633-303. It describes the data to be summarized and analyzed, including specifics of the statistical analyses to be performed.

This interim statistical analysis plan (SAP) is based on protocol amendment 2, dated 17 March 2017.

## 3. STUDY OBJECTIVES

### 3.1. PRIMARY OBJECTIVE

The primary objective of this interim analysis is to evaluate the retrospective safety and tolerability data of teduglutide treatment in the SHP633-303 study, which enrolled pediatric subjects with Short Bowel Syndrome (SBS) who completed TED-C13-003.

### 3.2. SECONDARY OBJECTIVE

The secondary objective of this interim analysis is to evaluate the efficacy data of teduglutide treatment in the SHP633-303 study, which enrolled pediatric subjects with SBS who completed TED-C13-003.

## 4. STUDY DESIGN

### 4.1. GENERAL DESCRIPTION

This is a Phase 3, retrospective and prospective, open-label, long-term extension study to evaluate the safety and efficacy of teduglutide in pediatric subjects who completed the TED-C13-003 study (the core study). At the time of entry into the TED-C13-003 study, subjects were less than 18 years of age, were dependent on parenteral nutrition to provide at least 30% of their caloric or fluid needs, and had not been able to significantly reduce parenteral support (PS) for at least 3 months prior to enrollment. During the core study, pediatric subjects were entered into one of three teduglutide dosing cohorts: 0.0125 mg/kg/day, 0.025 mg/kg/day, or 0.05 mg/kg/day, based on the timing of their enrollment in the study, or a

Document: \\quintiles.net\Enterprise\Apps\sasdata\SASa\sas\Shire\Teduglutide\ZXA48914\Biostatistics\Documentation\Protocol\SHP633-303\_Retrospective\_SAP\_Final\_V1.0\_20171013  
Author: [REDACTED] Version Number: Final V1.0  
Version Date: 13Oct2017

Template No: CS\_TP\_BS016 – Revision 3  
Effective Date: 01May2012

Reference: CS\_WI\_BS005

Copyright © 2012 Quintiles Transnational Corp. All rights reserved.  
The contents of this document are confidential and proprietary to Quintiles Transnational Corp. Unauthorized use, disclosure or reproduction is strictly prohibited.

standard of care SOC cohort. The teduglutide dosing cohorts were filled in a sequential manner.

Approximately 40 subjects who completed the core study are expected to enroll in this extension study (SHP633-303). When signing the informed consent form (ICF) for this study, subjects can choose to participate in both retrospective and prospective portions of the study or only retrospective data collection. After informed consent/assent is obtained, study eligibility will be assessed for all subjects.

To evaluate efficacy and safety from the time subjects completed the core study to the time they enter this extension study, retrospective data collection is planned for this study. The retrospective data collection will consist of specific safety and efficacy measures that were completed in the course of the subject's standard medical care between the date of the TED-C13-003 end of study (EOS), which is the final scheduled visit 4 weeks after the end of treatment, and the date the ICF (and if applicable, informed assent) is signed for this study. Retrospective PS and growth data will be captured in 12-week intervals, with the first 12-week interval beginning at the TED-C13-003 EOS. All available retrospective data should be captured in the corresponding electronic case report forms (eCRFs). The following data will be collected:

- Teduglutide use (as prescribed)
- Parenteral support (as prescribed)
- Growth (height, head circumference [up to 36 months of age], weight)
- End dates for adverse events (AEs) ongoing at the time of TED-C13-003
- All nonserious AEs related to teduglutide
- All adverse events of special interest (AESIs)
- All serious adverse events (SAEs)

In addition to this retrospective data collection, prospective study assessments of safety and efficacy will be completed as a part of this study. The prospective data analysis will be described in the prospective SAP for this study.

## 4.2. SCHEDULE OF EVENTS

The assessments completed as part of the retrospective data collection period can be found in Table 1-1 and Section 7.1.1 of the protocol. For subjects who only consent to retrospective data collection, these procedures are all that will be completed.

Document: \\quintiles.net\Enterprise\Apps\sasdata\SASa\sas\Shire\Teduglutide\ZXA48914\Biostatistics\Documentation\Protocol\SHP633-303\_Retrospective\_SAP\_Final\_V1.0\_20171013  
Author: [REDACTED] Version Number: Final V1.0  
Version Date: 13Oct2017

Template No: CS\_TP\_BS016 – Revision 3  
Effective Date: 01May2012

Reference: CS\_WI\_BS005

Copyright © 2012 Quintiles Transnational Corp. All rights reserved.  
The contents of this document are confidential and proprietary to Quintiles Transnational Corp. Unauthorized use, disclosure or reproduction is strictly prohibited.

#### 4.3. CHANGES TO ANALYSIS FROM PROTOCOL

There is no change of analysis from the protocol.

### 5. PLANNED ANALYSES

The following analyses will be performed for this study:

- Interim Analysis for Retrospective Data
- Final Analysis

The interim analyses identified in this SAP using retrospective data will be performed by Quintiles Biostatistics following sponsor authorization of this statistical analysis plan and analysis sets. The final analyses including prospective data will be performed following the sponsor-authorized SAP and analysis sets for the CSR.

### 6. ANALYSIS SETS

Analysis of efficacy and safety endpoints will be performed based on the analysis sets defined in this section and as specified for each endpoint throughout this SAP.

#### 6.1. ALL RETROSPECTIVE SUBJECTS [RETRO]

Retrospective subjects (RETRO) are all subjects who consented to the SHP633-303 study and provided data for the retrospective portion of the protocol. Subjects will be classified in treatment groups based on whether they received teduglutide in the core study TED-C13-003 and/or during the retrospective observation period in this study:

- TED/NTT – includes subjects who took teduglutide in the core study but not during the retrospective period of this study;
- TED/TED - includes subjects who took teduglutide in the core study and during the retrospective period of this study;
- ANY TED – includes subjects who took any teduglutide in the core study or during the retrospective period of this study.

No treatment-naïve patients in core study TED-C13-003 enrolled in the extension study SHP633-303, so the treatment groups associated with the NTT in the core study are removed

Document: \\quintiles.net\Enterprise\Apps\sasdata\SASa\sas\Shire\Teduglutide\ZXA48914\Biostatistics\Documentation\Protocol\SHP633-303\_Retrospective\_SAP\_Final\_V1.0\_20171013  
Author: [REDACTED] Version Number: Final V1.0  
Version Date: 13Oct2017

Template No: CS\_TP\_BS016 – Revision 3  
Effective Date: 01May2012

Reference: CS\_WI\_BS005

Copyright © 2012 Quintiles Transnational Corp. All rights reserved.  
The contents of this document are confidential and proprietary to Quintiles Transnational Corp. Unauthorized use, disclosure or reproduction is strictly prohibited.

from the statistical analysis.

## 7. GENERAL CONSIDERATIONS

### 7.1. REFERENCE START DATE AND STUDY DAY

Study Day will be calculated from the reference start date, and will be used to show start/stop day of assessments and events.

Reference start date of retrospective period is defined as the final scheduled visit of TED-C13-003 for the safety variables, while reference start date of core study is defined as the baseline visit for the growth and efficacy variables.

Study days before the reference start date will be negative.

If the date of the event is on or after the reference start date then:

Study Day = (date of event – reference start date) + 1.

If the date of the event is prior to the reference start date then:

Study Day = (date of event – reference start date).

In the situation where the event date is partial or missing, the date will appear partial or missing in the listings, and Study Day will be missing.

### 7.2. BASELINE

Unless otherwise specified, baseline is defined as baseline visit in the core study TED-C13-003.

### 7.3. WINDOWING CONVENTIONS

Retrospective PS and growth data will be captured in 12-week intervals, with the first 12-week interval beginning at the TED-C13-003 EOS. There will be no windowing of scheduled intervals based on study day.

### 7.4. STATISTICAL TESTS

Due to the limited size of the study population descriptive statistics will be used with a goal of summarizing the sample. As such, no claims of significance will be made for any of the data.

Document: \\quintiles.net\Enterprise\Apps\sasdata\SASa\sas\Shire\Teduglutide\ZXA48914\Biostatistics\Documentation\Protocol\SHP633-303\_Retrospective\_SAP\_Final\_V1.0\_20171013  
Author: [REDACTED] Version Number: Final V1.0  
Version Date: 13Oct2017

Template No: CS\_TP\_BS016 – Revision 3  
Effective Date: 01May2012

Reference: CS\_WI\_BS005

Copyright © 2012 Quintiles Transnational Corp. All rights reserved.  
The contents of this document are confidential and proprietary to Quintiles Transnational Corp. Unauthorized use, disclosure or reproduction is strictly prohibited.

Continuous variables, including those assessed on a discrete scale, will be summarized using descriptive statistics including number of subjects, mean, median, standard deviation, maximum, and minimum. For categorical variables, statistical summaries will include number of subjects and percentages.

## 7.5. COMMON CALCULATIONS

For quantitative measurements, change from baseline will be calculated as:

Test Value at Visit X – Baseline Value

Percent change from baseline will be calculated as:

(Test Value at Visit X – Baseline Value) / Baseline Value \*100

Change (or percent change) from baseline tables will be calculated based on the number of subjects in the treatment group with a non-missing value at baseline and at the time point being analyzed.

## 7.6. SOFTWARE VERSION

All analyses will be conducted using SAS version 9.4 or higher.

# 8. STATISTICAL CONSIDERATIONS

## 8.1. ADJUSTMENTS FOR COVARIATES AND FACTORS TO BE INCLUDED IN ANALYSES

No adjustments for covariates are planned for the statistical analyses.

## 8.2. MULTICENTER STUDIES

This study will be conducted by multiple investigators at multiple centers internationally.

## 8.3. MISSING DATA

Missing data will in general not be imputed. All available data will be included in the safety analysis.

Document: \\quintiles.net\Enterprise\Apps\sasdata\SASa\sas\Shire\Teduglutide\ZXA48914\Biostatistics\Documentation\Protocol\SHP633-303\_Retrospective\_SAP\_Final\_V1.0\_20171013  
Author: [REDACTED] Version Number: Final V1.0  
Version Date: 13Oct2017

Template No: CS\_TP\_BS016 – Revision 3  
Effective Date: 01May2012

Reference: CS\_WI\_BS005

Copyright © 2012 Quintiles Transnational Corp. All rights reserved.  
The contents of this document are confidential and proprietary to Quintiles Transnational Corp. Unauthorized use, disclosure or reproduction is strictly prohibited.

## 8.4. MULTIPLE COMPARISONS/ MULTIPLICITY

No hypothesis testing will be conducted. Therefore, there will be no adjustment for alpha level.

## 8.5. EXAMINATION OF SUBGROUPS

No subgroup analysis will be performed for retrospective data.

## 9. OUTPUT PRESENTATIONS

[APPENDIX 1](#) shows conventions for presentation of data in outputs. The output templates provided together with this SAP describe the presentations for the analyses of this study based on Shire internal standards TFLs4ShireFinalV6.0. The format and content of the summary tables, figures and listings (TFLs) will be provided by Quintiles Biostatistics.

## 10. ENROLLMENT

All subjects who provide informed consent for retrospective data collection period will be accounted for in this interim analysis. The subjects will be encouraged to consent to participate in the prospective period of the study. However, subjects may consent to retrospective data collection only.

## 11. DEMOGRAPHIC AND OTHER BASELINE CHARACTERISTICS

Demographic data and other baseline characteristics will be presented.

The following demographic and other baseline characteristics will be summarized:

- Age (years) at baseline of TED-C13-003.
- Age Group – Age is categorized in pre-defined groups: < 13, 13 to <17
- Sex
- Race
- Ethnicity

Document: \\quintiles.net\Enterprise\Apps\sasdata\SASa\sas\Shire\Teduglutide\ZXA48914\Biostatistics\Documentation\Protocol\SHP633-303\_Retrospective\_SAP\_Final\_V1.0\_20171013

Author: [REDACTED]

Version Number:

Final V1.0

Version Date:

13Oct2017

Template No: CS\_TP\_BS016 – Revision 3

Effective Date: 01May2012

Reference: CS\_WI\_BS005

Copyright © 2012 Quintiles Transnational Corp. All rights reserved.

The contents of this document are confidential and proprietary to Quintiles Transnational Corp. Unauthorized use, disclosure or reproduction is strictly prohibited.

- Weight Z-score at baseline of TED-C13-003
- Height Z-score at baseline of TED-C13-003
- Body Mass Index (BMI) Z-score at baseline of TED-C13-003
- Head Circumference Z-score at Baseline (only for subjects who are <= 36 months of age) of TED-C13-003

The demographic data collected in the eCRF will be listed by subject.

### **11.1. DERIVATIONS**

- BMI (kg/ m^2) = 10000\*weight (kg)/ height (cm)
- Z-score of weight, height, BMI and head circumference will be calculated based on the method described in Section 14.2.1.

## **12. EFFICACY OUTCOMES**

Efficacy analyses for PS based on 12-week intervals prescribed data during the retrospective observation period will be performed. The descriptive statistics of efficacy outcomes will be summarized by treatment group as defined in Section 6.1. The listings for efficacy measures which are collected on the eCRF forms will be provided.

### **12.1. EFFICACY ENDPOINTS**

#### **12.1.1. EFFICACY VARIABLES & DERIVATIONS**

PS investigator-prescribed data will be reported in the Parenteral Support (Retrospective Period) and Historical Teduglutide Treatment (Retrospective Period) eCRF. Data collected include weekly volume, calories, average days per week, and hours per day of prescribed PS. Prescribed data are the last representative PS prescription during each 12-week interval throughout the retrospective period, with the first 12-week interval beginning at the TED-C13-003 EOS visit, and at the beginning and end of any teduglutide treatment. Any tedgulutide was used in the 12-week interval will be indicated in the summary listing. The start date and end date of each 12-week interval will be derived based on the end of study date of TED-C13-003. The start date of the first 12-week interval will be the end of study date of TED-C13-003 + 1. The end date of the interval will be the start date of the interval + 12\*7. If the teduglutide

Document: \\quintiles.net\Enterprise\Apps\sasdata\SASa\sas\Shire\Teduglutide\ZXA48914\Biostatistics\Documentation\Protocol\SHP633-303\_Retrospective\_SAP\_Final\_V1.0\_20171013

Author: [REDACTED] Version Number: Final V1.0  
Version Date: 13Oct2017

Template No: CS\_TP\_BS016 – Revision 3  
Effective Date: 01May2012

Reference: CS\_WI\_BS005

Copyright © 2012 Quintiles Transnational Corp. All rights reserved.  
The contents of this document are confidential and proprietary to Quintiles Transnational Corp. Unauthorized use, disclosure or reproduction is strictly prohibited.

use period (from prescription start date to prescription stop date) falls into any 12-week intervals, the 12-week intervals will be marked 'Yes' in the teduglutide used column.

The calculation of average daily prescribed PS volume and caloric intake normalized to weight will follow the formula below:

Average daily value = (prescribed weekly PS parameter / 7) / last available weight prior to the 12-week interval.

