#### 12.1.1.1. ≥ 20% Reduction in PS volume

PS volume reduction at each 12-week interval compared to the baseline of the core study TED-C13-003 will be calculated using average daily values. The number and percentage of subjects who achieve at least a 20% reduction in PS volume (mL/kg/day) at each 12-week interval during the retrospective observation period will be summarized.

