#### 12.1.1.2. Change and percent change from baseline in PS volume and intake calories

Changes and percent change are calculated following common calculations in Section 7.5. The baseline is defined as the PS prescribed data collected at the baseline of the core study TED-C13-003.

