#### **14.2. GROWTH DATA**

The last representative value for height and weight during each 12-week interval throughout the retrospective observation period will be captured in the Growth Data (Retrospective Period) form of eCRF as well as the head circumference for subjects 36 months of age and younger at the time the data was collected.

Document: \\quintiles.net\Enterprise\Apps\sasdata\SASa\sas\Shire\Teduglutide\ZXA48914\Biostatistics\Documentation\Protocol\SHP633-303\_Retrospective\_SAP\_Final\_V1.0\_20171013  
Author: [REDACTED] Version Number: Final V1.0  
Version Date: 13Oct2017

Template No: CS\_TP\_BS016 – Revision 3  
Effective Date: 01May2012

Reference: CS\_WI\_BS005

Copyright © 2012 Quintiles Transnational Corp. All rights reserved.  
The contents of this document are confidential and proprietary to Quintiles Transnational Corp. Unauthorized use, disclosure or reproduction is strictly prohibited.

The following growth data will be reported for retrospective observation period:

- Height (cm)
- Weight (kg)
- Head circumference (cm) for subjects  $\leq$  36 months of age

The following parameters will be derived during each 12-week interval:

- BMI ( $\text{kg}/\text{m}^2$ ) [when both height and weight are available in the interval]
- Height Z-score
- Weight Z-score
- BMI Z-score
- Head circumference Z-score for subjects  $\leq$  36 months of age

Descriptive statistics will be used to summarize growth data and derived parameters in actual value and change from baseline at 12-week intervals where associated parameters are collected. A mean  $\pm$  SE plot and a data listing will also be provided.

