### 16.1. EFFICACY ENDPOINTS

#### 16.1.1. EFFICACY VARIABLES & DERIVATIONS

The efficacy endpoints will be analyzed in two ways: 1) based on the subject diary data (also referred to as "actual"), and 2) based on the investigator-prescribed data (referred to as "prescribed"). PS will be reported in both subject diary data and the investigator-prescribed data in the eCRF. Investigator-prescribed data are the most recent PS prescription (prescription adjustments) prior to or on the date of visit, captured in the PS adjustments eCRFs. Data collected include prescribed weekly total kilocalories, volume, number of days per week, and average hours per day. PS diary data are collected 2 weeks prior to all scheduled site visits (except at pre-treatment visit) in the Intake Diary eCRFs over 24-hour periods that start on the assigned date. Depending on the time of day at which the 24 hour period begins, which can vary by subject, overnight PS volumes after midnight may be associated with prior the date. Data collected include actual PS total infusion duration, total volume and total kilocalories on the assigned date.

The calculation of average daily prescribed PS volume/caloric intake normalized to weight will follow the formula below:

Average daily value = (prescribed weekly PS parameter / 7) / last available weight prior to or on the date of visit.

The calculation of average daily actual PS will be based on the daily support recorded in

Document: \\quintiles.net\Enterprise\Apps\sasdata\SASa\sas\Shire\Teduglutide\ZXA48914\Biostatistics\Documentation\SAP\SHP633-303\_SAP\_Draft\_V1.0\_20171023

Author: [REDACTED] Version Number: Draft V1.2  
Version Date: 16Jan2018

Template No: CS\_TP\_BS016 – Revision 3  
Effective Date: 01May2012

Reference: CS\_WI\_BS005

Copyright © 2012 Quintiles Transnational Corp. All rights reserved.  
The contents of this document are confidential and proprietary to Quintiles Transnational Corp. Unauthorized use, disclosure or reproduction is strictly prohibited.

subjects' diaries within 7 days prior to the date of each scheduled visit. If more than 2 days' values in a week are missing, the average daily value will not be calculated and will be assigned as missing. The same strategy will be used to calculate all other average diary parameters. The calculation of actual PS volume normalized to weight will follow the formula below:

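### Retrospective PS per kg divides a prescription from within each 12-week interval by a weight taken before that interval, so the ≥20% cut-off moves with weight change

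*SAP*

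**What the plan says.** Retrospective SAP:

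- Section 12.1.1 defines the numerator: "Prescribed data are the last representative PS prescription during each 12-week interval throughout the retrospective period". It then gives the weight-normalised value: "Average daily value = (prescribed weekly PS parameter / 7) / last available weight prior to the 12-week interval".
- The interval is a dated span and not a time point: "The start date and end date of each 12-week interval will be derived based on the end of study date of TED-C13-003".
- Section 4.1 puts PS and growth on the same grid: "Retrospective PS and growth data will be captured in 12-week intervals, with the first 12-week interval beginning at the TED-C13-003 EOS". Section 14.2 confirms that a weight is collected in each interval: "The last representative value for height and weight during each 12-week interval throughout the retrospective observation period will be captured". Section 14.2.1 already pairs height and weight from the same interval to derive BMI.
- Section 12.1.1.1 builds the responder endpoint on the normalised values, counting subjects with "at least a 20% reduction in PS volume (mL/kg/day) at each 12-week interval during the retrospective observation period".
- Section 12.1.1.2 uses PS volume and calories for change and percent change. For baseline it says "The baseline is defined as the PS prescribed data collected at the baseline of the core study TED-C13-003", without naming the weight that goes with it.

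Prospective SAP, section 16.1.1: the same prescribed variable, compared with the same core-study baseline, is divided by the "last available weight prior to or on the date of visit".

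**The concern.** Read as written, the retrospective rule excludes every weight taken within the interval, even one recorded on the day of the prescription. From the second interval on, the weight used can come from anywhere in the preceding interval, or from further back if that interval has none. All subjects were under 18 at entry to the core study (section 4.1), so their weight can be expected to change over such a lag.

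PS is judged per kg because needs scale with body size. A weight that is too low for the date of the prescription inflates mL/kg/day and understates the reduction; a weight that is too high does the opposite. The error therefore has a direction wherever subjects gain or lose weight. It need not be equal in TED/NTT and TED/TED if their weight courses differ. At stake are the ≥20% responder counts, the change and percent change in PS volume and calories, and comparability between the retrospective and prospective summaries. The SAP gives no reason for preferring the older weight.

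**Working it through.** The SAP states no figure for this point, so there is nothing to reproduce. The check is algebra plus assumed weight changes.

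**Inputs.** From the retrospective SAP: the formula, the numerator and the interval (section 12.1.1), and the 20% threshold (section 12.1.1.1). Assumed: the weight change g, and a core-baseline value B (mL/kg/day) based on a weight from about baseline.

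**Lag.** Take intervals of 84 days.
- SAP rule, extreme case: weight on the first day of the previous interval, prescription on the last day of the current one. Lag = 2 × 84 − 1 = 167 days, about 24 weeks.
- If both values fall near the ends of their intervals, the lag is about 12 weeks.
- Same-interval weight: the gap is at most 84 − 1 = 83 days, about 12 weeks.

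**Effect on the cut-off.** Let W0 be the weight before the interval, Wp = W0(1+g) the weight at the prescription, V the weekly volume, and r the reduction using Wp, so that V/(7·Wp) = (1−r)·B. The SAP value is V/(7·W0) = (1−r)(1+g)·B.
- SAP-computed reduction = 1 − (1−r)(1+g) = r − g(1−r). The error is g(1−r).
- A subject counts as a responder if (1−r)(1+g) ≤ 0.80, that is, if r ≥ 1 − 0.80/(1+g).

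| Assumed g | Effective cut-off |
|---|---|
| −3% | 1 − 0.80/0.97 = 17.5% |
| 2% | 1 − 0.80/1.02 = 21.6% |
| 4% | 1 − 0.80/1.04 = 23.1% |
| 8% | 1 − 0.80/1.08 = 25.9% |

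Understatement of the percent reduction, in percentage points, from g(1−r):

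| g | r = 0% | 20% | 50% | 75% | 100% |
|---|---|---|---|---|---|
| 2% | 2.0 | 1.6 | 1.0 | 0.5 | 0 |
| 4% | 4.0 | 3.2 | 2.0 | 1.0 | 0 |
| 8% | 8.0 | 6.4 | 4.0 | 2.0 | 0 |

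**Worked case (assumed values).** Baseline 80 mL/kg/day; 10.0 kg before the interval; 10.4 kg at the prescription (g = 4%); 4659.2 mL/week.
- Daily volume: 4659.2/7 = 665.6 mL.
- At 10.4 kg: 64.0 mL/kg/day, a 20.0% reduction, responder.
- SAP rule at 10.0 kg: 66.56 mL/kg/day; 1 − 66.56/80 = 16.8%, non-responder.

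**Check on the alternative.** The same-interval weight may post-date the prescription. If it is higher by a fraction h, the cut-off becomes 1 − 0.80(1+h): 19.2% at h = 1% and 18.4% at h = 2%.

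Suppose weight rises linearly by a total fraction G between the two weights and the prescription falls at fraction f of that span. The relative errors are fG under the SAP rule and (1−f)G/(1+G) under the alternative. They are equal at f = 1/(2+G): 0.495 for G = 2%, 0.490 for 4%, 0.481 for 8%. Beyond that point, roughly the later half of the span, the same-interval weight is closer.

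**The case against.** The strongest case against has four parts.

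- **The prospective SAP is not uniform.** Its section 16.1.1 divides diary PS by the last weight before the visit, so a prior-weight denominator also appears there. The retrospective period has no study visits either, so a visit-date rule does not carry over directly. This stands as a limit on the consistency argument. But the diary rule is anchored to a visit date, whereas the retrospective rule pushes the weight back before a whole 12-week interval.
- **The same-interval weight is not always better.** If the prescription was set early in the span, the SAP rule has the smaller error. This is correct, and the SAP does not say where prescriptions fall. Still, both the prescription and the weight are defined as the last representative value of the same interval, which makes them the natural pair.
- **The size is assumed.** Every g is hypothetical, the 24-week lag is an extreme, and the baseline weight is not stated; if the baseline prescription were also divided by an older weight, part of the error could cancel. This stands. The figures show sensitivity and are not estimates for this trial.
- **The impact is small.** The analysis is descriptive, without hypothesis tests (sections 7.4 and 8.4), and efficacy is the secondary objective (section 3.2). Under weight gain the rule is conservative, and the collected data are listed, so another normalisation can be checked. This limits the weight of the point but does not remove it: under weight loss the rule overstates the reduction, and the SAP does not offer conservatism as its reason.

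**Conclusion.** The concern holds. The rule as written pairs a prescription from inside the interval with a weight from before it, although a weight from the same interval is planned. For assumed weight gains of 2% to 8% over the lag, a subject needs a true reduction of 21.6% to 25.9% to be counted as a 20% responder; for a 3% loss, 17.5% suffices. Under weight gain, only subjects whose true reduction lies between 20% and the shifted cut-off change status. The percent-change summaries shift for everyone still on PS whose weight changed over the lag.

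The error is small where the prescription was set soon after the earlier weight, and zero for subjects fully weaned. Hours per day and days per week are not weight-normalised and are unaffected. The result rests on the assumed g and on a baseline value that uses a weight from about baseline. It is an avoidable, directional bias in a descriptive secondary analysis: worth correcting, but no threat to the study's primary objective.

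**What to change.** In retrospective SAP section 12.1.1, replace the denominator with the representative weight captured in the same 12-week interval; where both dates are recorded, use the weight closest to the prescription date. Fall back on the last earlier weight only if the interval has none. Add that the core-study baseline prescription is divided by the baseline-visit weight. This brings the rule closer to the prospective treatment of prescribed PS, where the prescription in force is divided by a weight up to and including the visit date.

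The cost is one sentence and a merge by subject and interval. No new data are needed, and the basic rule needs no dates. The downside is that the interval weight may post-date the prescription, which in a growing child lowers the cut-off slightly (19.2% or 18.4% in the cases shown above).
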